4. STUDY DESIGN

4.1 General Design

4.1.1 Phase 1

The objective of this study is to determine the maximum tolerated dose (MTD) of the combination of cobimetinib, atezolizumab, and hydroxychloroquine. We will evaluate three dose combinations. Patients will be treated with combination therapy at the designated dose levels depicted in Table 1, based on a 28 day cycle (Section 7.3). The MTD is defined as the dose associated with a target probability of dose limiting toxicity of 0.30. The primary endpoint is DLT in the first cycle of treatment.

Columbia University Irving Medical Center
Herbert Irving Comprehensive Cancer Center
AAAS4165_Version Date: 07/07/2021

Given that cobimetinib is approved at a dose of 60 mg orally daily and hydroxychloroquine was well tolerated at 600 mg orally twice daily, we feel that the combination will be well tolerated (Wolpin et al., 2014). Cobimetinib and atezolizumab were tested in advanced colorectal cancer in IMblaze370, a large randomized phase 3 clinical trial (Eng et al., 2019) with proportion of patients experiencing grade 3 and over adverse events similar to those who received the FDA approved Regorafenib. Subjects will receive cobimetinib in cohort 1 and 2 at a lower dose (40mg oral daily) compared to that tested in IMblaze370 (60mg oral daily). Given that, other than ocular and hepatic toxicity, hydroxychloroquine has little to no overlapping adverse events with cobimetinib and atezolizumab, we do not anticipate significant toxicities with this combination at the doses being tested. Ocular toxicities with hydroxychloroquine are observed at high cumulative doses and will be monitored by required scheduled ophthalmological evaluations throughout the study period. We will initiate Phase 1 at dose level 1 using a combined 3+4 and time-to-event continual reassessment method (TITE-CRM). Table 1. Cohort dose levels.

| Patient No. | Dose Level | Hydroxychloroquine (mg) (oral; 1200mg/day; Days 1-28) | Cobimetinib (mg) (oral; 40-60mg/day; Days 1-21) | Atezolizumab (mg) (IV; 840mg every two weeks) |
|------------------|------------|---|---|---|
| 1, 2, 3 | 1 | 600mg twice per day | 40mg | |
| 4, 5, 6 | 2 | 600mg twice per day | 40mg | 840mg |
| 7, 8, 9 10-18 | 3 | 600mg twice per day TITE-CRM | 60mg | 840mg |

Phase I Statistical Considerations

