The MTD will be estimated using a two-stage time to event continual reassessment method (TITE-CRM), whereby in the first stage patients will be assigned to 3-patient cohorts (see table below) in the absence of DLT. However, once a DLT is observed, we will initiate the second stage and patients will be assigned using the TITE-CRM. The initial design for the two stage was obtained using the method by Jia, et al (Jia, Ivanova, & Lee, 2017).

Table 2. Selection probabilities and average expected number of patients assigned to each dose based on the two stage TITE-CRM (N=18)

| Doses Level | | 1 | 2 | 3 |
|-------------|-------------------------|-----|-----|-----|
| Scenario 1 | DLT rate | 30% | 45% | 55% |
| | P(Selection) | 74% | 23% | 4% |
| | Average Number Assigned | 11 | 4 | 3 |

Columbia University Irving Medical Center
Herbert Irving Comprehensive Cancer Center
AAAS4165_Version Date: 07/07/2021

The advantage of the TITE-CRM is that it uses the patient's partial information before a complete follow-up is achieved. As a result, we can conduct the trial in a continuous fashion without having patients be turned away due to waiting time. The TITE-CRM will use an empirical dose-toxicity model, with a sample size

| | DLT rate | 15% | 30% | 45% |
|-------------------|--------------------------------|-----|-----|-----|
| Scenario 2 | P(Selection) | 24% | 53% | 23% |
| | Average Number Assigned | 6 | 6 | 6 |
| Scenario 3 | DLT rate | 5% | 15% | 30% |
| | P(Selection) | 1% | 25% | 74% |
| | Average Number Assigned | 2 | 5 | 11 |

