Final decisions on determination of DLTs will be made in consultation with the Principal Investigator. The Principal Investigator may decide not to further dose escalate based on clinical judgement.

DLTs are considered AEs of special interest, and require close monitoring and rapid communication with the Principal Investigator. A DLT may be serious or nonserious. The rapid reporting of DLTs allows ongoing surveillance of these events in order to prevent enrollment of subjects at inappropriate dose levels, therefore, DLTs will be required to be reported to the study email [contact] **within 24 hours** to the lead site by memo signed by the Affiliate Site PI/Treating Investigator. DLTs should also be reported in Velos. Please refer to Section 14.2 for Data Reporting Guidelines.

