13.5 Clinical Monitoring

An ssDSMP is required for all investigator initiated trials, wherein CUIMC HICCCC DSMC is serving as the DSMC of record.

Ongoing monitoring of the clinical study for protocol and GCP compliance will be conducted on a quarterly basis by the CPDM Compliance Core on behalf of the HICCC DSMC. Quarterly

Columbia University Irving Medical Center
Herbert Irving Comprehensive Cancer Center
AAAS4165_Version Date: 07/07/2021

monitoring will ensure data quality and verify source documents for all enrolled subjects related to dose limiting toxicity, all response assessments and RECIST/imRECIST forms, study drug administration including, but not limited to pill accountability, duration of response, date of disease progression, resolution of treated related AEs, subsequent treatments, and survival. This report will be submitted to the Sponsor-Investigator and study statistician on a quarterly basis. Delinquent or discrepant data will be rectified within 4 weeks of notification and the quarterly report amended and resubmitted by the DSMP office. Additionally, the Compliance Oversight Committee of the IRB at Columbia University Medical Center may audit the study at any time per institutional policies and procedures. The investigator-sponsor and Columbia University Medical Center will permit direct access of the study monitors and appropriate regulatory authorities to the study data and to the corresponding source data and documents to verify the accuracy of this data.

A risk-based approach will be used by the Compliance Core to determine the frequency, number of subject charts, and data elements to be monitored. This trial will utilize a study-specific Data Safety Monitoring Plan (which is to be reviewed and acknowledged by the HICCC DSMC).

The Compliance Coordinator will review the study status and summarize enrollment, toxicities, SAEs/UPs, dose escalation, statistical endpoints (e.g., stopping rules), etc. for the full DSMC membership at the regularly scheduled meetings.

13.5.1 Internal On-site Monitoring:

- Initial, recurrent, and close-out on-site monitoring visits will also be conducted at remote clinical sites, as appropriate/feasible. Other sites will have monitoring performed remotely (see below for further details).
- The Compliance Coordinator will communicate with the site coordinator/site Principle Investigator to schedule the monitoring visits and arrange for access to study materials and documentation.

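### Phase 1 has no pre-specified toxicity boundary and no way to conclude that there is no MTD, and Table 2 never tests a level 1 above the 30% target

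*Combined protocol and SAP*

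**What the plan says.** Section 4.1.1 of the combined protocol and SAP sets the target: "The MTD is defined as the dose associated with a target probability of dose limiting toxicity of 0.30". On the levels it says: "We will evaluate three dose combinations". Table 1 starts at level 1, which is cobimetinib plus hydroxychloroquine without atezolizumab, and lists no cohort level beneath it.

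Assignment runs in two stages. At the start, "in the first stage patients will be assigned to 3-patient cohorts (see table below) in the absence of DLT". Then "once a DLT is observed, we will initiate the second stage and patients will be assigned using the TITE-CRM". Accrual continues to 18 evaluable patients (4.1.1.2). The written limits are no dose skipping, no escalation directly after a DLT and at least one week between second-stage patients. Section 4.1.1.1 adds one discretion: "The Principal Investigator may decide not to further dose escalate based on clinical judgement".

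Section 4.1.1.3 reports the model estimate of the DLT probability at each dose with a 90% interval, and the observed rates. It ties no decision to them. Table 2 simulates three scenarios, with level 1 at 30%, 15% and 5%. The text then claims correct selection with probability over 53% whatever the scenario.

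Section 13.3 gives the HICCC DSMC general toxicity oversight. Section 13.5 lists, among the items summarised for it, "dose escalation, statistical endpoints (e.g., stopping rules".

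**The concern.** A continual reassessment method without a safety boundary must always choose one of its levels. If the lowest level is already above target, the written rule keeps assigning it and ends by naming it. The restrictions on skipping and escalation, and the investigator's option not to escalate, all act upward from level 1. None acts on level 1 itself.

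The MTD is the sole primary objective of Phase 1. Followed exactly, the rule could return a dose well above the 30% target and treat nearly all 18 patients there. Table 2 gives no view of this behaviour, because its worst case puts level 1 exactly on target and its rows leave no share for selecting no dose. They total 74 + 23 + 4 = 101% (rounding), 24 + 53 + 23 = 100% and 1 + 25 + 74 = 100%.

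**Working it through.** **Inputs from Section 4.1.1.** Target 0.30; three levels; 3-patient cohorts until the first DLT; empirical model; prior N(0, 1.34); 4-week DLT window; one arrival per week; DLT times uniform over the window; 18 patients; no skipping; no escalation directly after a DLT. The Synopsis puts the MTD at DLT by the end of Cycle 2; I used the 4 weeks on which Table 2 is based.

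**Assumptions.** The protocol gives no skeleton. The indifference-interval method with half-width 0.07 (half the width of the stated 18% to 32% range), target 0.30 and prior MTD at level 2 gives 0.169/0.300/0.443. The final selection rule is not written out; I took the usual one, the level whose estimate is closest to 0.30.

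**Step 1: reproduce Table 2 (8,000 simulated trials per scenario).**

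| Scenario (true DLT %) | Table 2 selection % | Simulated % |
|---|---|---|
| 1 (30/45/55) | 74 / 23 / 4 | 73.9 / 22.5 / 3.6 |
| 2 (15/30/45) | 24 / 53 / 23 | 22.4 / 53.5 / 24.1 |
| 3 (5/15/30) | 1 / 25 / 74 | 1.1 / 22.8 / 76.1 |

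Scenarios 1 and 2 agree within 2 points. Scenario 3 differs by 2.1 to 2.2 points; the standard error of the stated 74% from the protocol's 2,000 runs is √(0.74 × 0.26 / 2000) = 1.0 point. Table 2's average numbers assigned do not reproduce: in Scenario 1 I get 13.0/4.0/0.9 against 11/4/3.

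**Step 2: why level 1 is always chosen when it is too toxic.** Under the empirical model the estimate at level i is s_i^exp(b), where s_i is the skeleton value, so the estimates always rise with level. Once the level 1 estimate is above 0.30, levels 2 and 3 are further from 0.30, whatever the skeleton. With all 18 patients at level 1:

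| DLTs at level 1 | Estimates, levels 1/2/3 | Chosen |
|---|---|---|
| 9/18 | 0.49 / 0.62 / 0.72 | 1 |
| 11/18 | 0.59 / 0.70 / 0.79 | 1 |
| 18/18 | 0.90 / 0.93 / 0.96 | 1 |

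After 3 DLTs in the first 3 patients, the posterior probability that the level 1 rate exceeds 0.30 is about 0.975, and patient 4 is still assigned level 1.

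**Step 3: size under over-toxic scenarios, no boundary (3,000 trials each).**

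| True DLT % | Level 1 named MTD | No dose | Mean n at levels 1/2/3 | Mean DLTs |
|---|---|---|---|---|
| 50/60/70 | 98.9% | 0% | 16.9 / 1.0 / 0.1 | 9.1 |
| 60/70/80 | 99.9% | 0% | 17.6 / 0.4 / 0.0 | 10.9 |

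Check on the first row: 16.9 × 0.50 + 1.0 × 0.60 + 0.1 × 0.70 = 9.1. Other skeletons (half-width 0.05 or 0.08, prior MTD at level 1 or 3) give 97.9% to 98.8% and 99.9% to 100%. The result does not depend on the assumed skeleton.

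**Step 4: what a boundary could do (illustration).** Stop and declare no MTD if P(level 1 rate > 0.30) passes a cut-off, counting every trigger as a permanent stop.

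| Cut-off | Stop at 50/60/70 | Stop at 60/70/80 | Stop in Scenario 1 | Stop in Scenario 2 | Correct selection, Scenario 1 |
|---|---|---|---|---|---|
| 0.90 | 76% | 93% | 25% | 3% | 51% |
| 0.95 | 65% | 88% | 14% | 1% | 61% |
| 0.97 | about 54% | about 82% | 7–8% | about 0.4% | about 64% |

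With no rule, correct selection in Scenario 1 is about 73% to 74%. The 0.97 cut-off does not fire at 9/18 DLTs, where the posterior is about 0.956.

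**The case against.** The strongest reply is that people, not the algorithm, would stop a trial with this much toxicity. DLTs must be reported within 24 hours so that patients are not enrolled at unsuitable levels (4.1.1.1). The DSMC monitors every treated patient for toxicity, meets twice a month and can require modifications (13.3). A study-specific monitoring plan exists that is not in these documents (13.5). An estimate near 0.49 with its 90% interval would be plainly off target. Phase 2 cannot open without an amendment reviewed by the PRMC and IRB (4.1.2). All of this stands. A reader might infer that 18 patients would in practice be treated with 9 to 11 DLTs; the documents do not support that. They do show that nothing written says when such judgement must be exercised.

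Three other stronger readings also fail.

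- **That the plan has no stopping rules, so 13.5 refers to nothing.** The Phase 2 Simon designs in 4.1.2 are stopping rules, and 13.5 is not specific to Phase 1. What is missing is a Phase 1 toxicity rule.
- **That level 1 is an untried triplet likely to be toxic.** Level 1 is a doublet, and no document gives a DLT rate for it. The 61% Grade 3/4 rate in 3.1.4.2 is for cobimetinib with atezolizumab, and 4.1.1 gives the cobimetinib dose in that trial as higher than at level 1. Section 4.1.1 names only ocular and hepatic overlap for hydroxychloroquine.
- **That the sponsor's exact design has been reproduced.** The skeleton and selection rule are assumed, and the average assignments do not match.

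Nor do the rule-based labels supply a stop. Section 4.1.1 says "We will initiate Phase 1 at dose level 1 using a combined 3+4 and time-to-event continual reassessment method (TITE-CRM" and 10.1.3 calls the method a hybrid 3+3. These need reconciling, but under either label stage 1 ends at the first DLT and the TITE-CRM then governs.

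**Conclusion.** The concern holds for the written rule. Section 4.1.1 has no pre-specified Phase 1 toxicity boundary and no no-MTD outcome. With closest-to-0.30 selection, a level 1 with a true DLT rate of 50% or 60% would be named MTD in about 98% or over 99% of trials. The direction follows from the model itself; the exact percentages rest on the assumed skeleton, and the 50% and 60% rates are hypothetical. Because no Table 2 scenario puts level 1 above 30%, the statement that correct selection exceeds 53% in every possible scenario is not supported. It describes three scenarios in each of which one level sits exactly on target.

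**What to change.** 1. Add to 4.1.1 a statistical rule based on the TITE-CRM posterior probability that the level 1 DLT rate exceeds 0.30. Crossing the threshold would pause accrual for DSMC review, and a no-MTD conclusion would be allowed at the final analysis. The sponsor should choose the threshold by simulation with its own skeleton, and state both the skeleton and the final selection rule.
2. Add to Table 2 at least one scenario with level 1 above 30%, and a column for no dose selected.
3. Limit the claim about correct selection to the scenarios simulated.

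The cost is one rule and a re-run of existing simulations. The statistical price depends on the threshold. At 0.97, if every pause became a permanent stop, mean DLTs would fall from about 9.2 to 7.0 at 50/60/70% and from 10.9 to 6.8 at 60/70/80%. About 7–8% of trials would stop in Scenario 1, where level 1 is exactly on target, and correct selection there would fall from about 73% to 64%. About 0.4% would stop in Scenario 2. A 0.97 cut-off would still leave level 1 as the MTD at 9/18 DLTs, so it is an illustration and not a recommended value.

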4.1.1.2 Size/Accrual Rate

The planned accrual size is 18 evaluable patients, with an accrual rate of 4 patients per month.

4.1.1.3 Analysis of Primary Endpoints

The TITE-CRM will be used to estimate the probability of DLT at each dose. It will be reported along with the 90% probability interval. Moreover, the observed rate of DLT will be reported by dose level.

4.1.1.4 Analysis of Secondary and Exploratory Endpoints

The frequency of radiographic response will be documented with summary statistics at the estimated MTD and by dose level. Best overall response rate (CR+PR) will be calculated along with a 95% confidence interval.

Progression-free survival and overall survival curves will be generated using Kaplan-Meier methodology for all patients and those assigned to the estimated MTD at the end of the trial. Treatment-related toxicity will be reported by type, frequency, and severity according to the

Columbia University Irving Medical Center
Herbert Irving Comprehensive Cancer Center
AAAS4165_Version Date: 07/07/2021

National Cancer Institute Common Terminology Criteria for Adverse Events, version 5 (NCI, 2017).

Ten paired biopsies representing combination therapy with cobimetinib and hydroxychloroquine, with and without atezolizumab, will be performed. Once adequate tissue for exploratory analysis is procured from ten subjects, subsequent subjects may not need to undergo biopsies. Necessity will be determined by the principal investigator.

Patients will be required to obtain research-specific biopsies as follows:

- Baseline biopsy of a target lesion;
- Repeat biopsy during week 3 of Cycle 1 (for pharmacodynamic analysis);
- Optional biopsy at time of progression.

All biopsies will attempt to obtain 4-6 cores. Each core biopsy obtained from a patient will only be performed if deemed safe by the interventional radiologist. The interventional radiologist will cease from obtaining biopsies if he/she deems that additional biopsies performed from pulmonary nodules would put the patient at significant increased risk for biopsy-related complications, in which case the core biopsies should be limited to 3 cores, if feasible. Two of the cores will be processed for formalin fixation, 2 will be frozen in liquid nitrogen, and if additional core tissue is available, samples will be processed for generation of organoids and/or single cell DNA analysis for exploratory studies.

Changes in CD8⁺ T-cells, FoxP3⁺ T-reg, autophagy and other markers from pre-treatment biopsies at baseline to on-treatment biopsies will be summarized and reported as means, medians, standard deviations, and ranges, and compared using the Wilcoxon signed rank test for patients assigned to the MTD. These correlative studies will be considered exploratory in nature.

Statistical analysis of RNA-Seq expression data derived from samples of the treatment arms will be carried out in the R environment for statistical computing (RDC, 2016). In order to identify differentially expressed genes between the conditions, we will make use voom-limma framework (Ritchie et al., 2015). Briefly, linear models are fit for each gene to estimate the coefficients (= effect size) and their standard error. Empirical Bayes-moderated t-statistics and their associated p-values are then used to assess the significance of the observed expression changes.

In order to evaluate concerted differences of biologically related genes, single sample gene set enrichment will be employed via the GSVA R package (Hanzelmann, Castelo, & Guinney, 2013) which produces a gene-set by sample matrix with approximately normally distributed enrichment scores which can then be compared between treatment arms using for example linear models. Detailed statistical plan is as described in the manuscript [[name], submitted].

Columbia University Irving Medical Center
Herbert Irving Comprehensive Cancer Center
AAAS4165_Version Date: 07/07/2021

4.1.2 Phase 2

The phase 2 portion of the study will be amended after preliminary safety and efficacy results from phase 1 and other ongoing clinical trials have been analyzed and a summary incorporated within the protocol as an amendment including a rationale of the cohorts to be tested. The amendment will be submitted to the Scientific Review Committee (PRMC) and Institutional Review Board (IRB) at CUIMC for approval prior to activation of phase 2 portion of the study.

Three separate phase 2 studies will be conducted based on the differences in baseline response rate by disease subtype:

Cohort 1 – Advanced Pancreas Adenocarcinoma

Cohort 2 – Advanced Colorectal Adenocarcinoma

Cohort 3 – Histology Agnostic Adenocarcinoma

The primary outcome measure is best objective response by 16 weeks; that is, patients who achieve CR or PR within the first 16 weeks will be considered responders. Tumor response will be assessed by CT scans performed every 8 weeks using the Immune-Modified Response Evaluation Criteria in Solid Tumors (IM RECIST). We will use a Simon optimal 2-stage design for each disease subtype to allow for early stopping.

Advanced Pancreas Adenocarcinoma

For the advanced pancreas adenocarcinoma group, we assume an objective response rate of 16%, based on current therapy (Wang-Gillam et al., 2016). The study will enroll 23 patients in the first stage. If 5 or more patients respond in the first stage, the study will be expanded to a total of 67 patients. If a total of 16 or more patients respond, the combination will be considered promising in patients with advanced pancreatic adenocarcinoma. This optimal two-stage design assumes for a type 1 error of 0.05 and type 2 error of 0.20 to detect a difference of 16%, versus 30% in the best objective response rate by 16 weeks.

Metastatic Colorectal Adenocarcinoma

For the advanced colorectal adenocarcinoma group, we assume an objective response rate of 2%, based on current therapy (Grothey et al., 2013; Mayer et al., 2015). The study will enroll 20 patients in the first stage. If 2 or more patients respond in the first stage, the study will be expanded to a total of 34 patients. If a total of 3 or more patients respond, the combination will be considered promising in patients with advanced colorectal adenocarcinoma. This optimal two-stage design assumes for a type 1 error of 0.05 and type 2 error of 0.20 to detect a difference of 2%, versus 15% in the best objective response rate by 16 weeks.

Advanced Histology Agnostic Adenocarcinoma

For the histology agnostic adenocarcinoma group, we assume an objective response rate of 5%, based on current therapy, and given the inclusion criteria that subjects must have progressed on or are intolerant of all standard of care therapies that result in a median progression free survival benefit of ≥ 8 weeks or an overall response rate of $> 5\%$. The study will enroll 23 patients in the first stage. If 2 or more patients respond in the first stage, the study will be expanded to a total of

Columbia University Irving Medical Center
Herbert Irving Comprehensive Cancer Center
AAAS4165_Version Date: 07/07/2021

56 patients. If a total of 6 or more patients respond, the combination will be considered promising in patients with histology agnostic adenocarcinoma. This optimal two-stage design assumes for a type 1 error of 0.05 and type 2 error of 0.20 to detect a difference of 5% versus 15% in the best objective response rate by 16 weeks.

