1. STUDY OBJECTIVES

The overall objective of this study is to investigate the safety and preliminary efficacy of combination therapy with cobimetinib and hydroxychloroquine, with or without atezolizumab in patients with KRAS-mutated advanced malignancies. Given that the pre-clinical and clinical benefit from this combination is from within PDAC animal models and human subjects with PDAC and duodenal cancer, we will include at least 12 of the 18 evaluable subjects from PDAC

Columbia University Irving Medical Center
Herbert Irving Comprehensive Cancer Center
AAAS4165_Version Date: 07/07/2021

and/or colorectal malignancies. The phase 2 portion of the study will be amended after preliminary safety and efficacy results from phase 1 and other ongoing clinical trials have been analyzed and a summary incorporated within the protocol as an amendment including a rationale of the cohorts to be tested. The amendment will be submitted to the Scientific Review Committee at CUIMC for approval prior to activation of phase 2 portion of the study.

Specific objectives are:

Phase 1:

Primary: To estimate the maximum tolerated dose (MTD) of the combination of cobimetinib, atezolizumab, and hydroxychloroquine in KRAS-mutated advanced malignancies.

Secondary: To evaluate the safety profile of the combination of cobimetinib, atezolizumab, and hydroxychloroquine in KRAS-mutated advanced malignancies.

Phase 2:

Primary: To evaluate preliminary efficacy based on the objective response by 16 weeks of the combination cobimetinib, atezolizumab, and hydroxychloroquine treatment in KRAS-mutated advanced malignancies.

Secondary: To evaluate the progression-free time and overall survival and safety in patients treated with cobimetinib, atezolizumab, and hydroxychloroquine combined treatment in KRAS-mutated advanced malignancies.

Exploratory analysis objectives:

- Determine MEK and autophagy pathway inhibition and CD8+ T-cell infiltration within tumor specimens.
- Perform RNA seq analysis within tumor specimens.

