Each number represents an enrolled patient. Circled numbers depict time at which toxicity was experienced by that patient.

between 6 and 11 of the 18 patients will be assigned the MTD.

To illustrate the method using an example, Figure 5 displays a simulation of a sample design using the method based on scenario 2 (see Table 2), where the true MTD is dose level 2. In this simulated example, the recommended dose level is 2. The first three patients are assigned to dose level 1 in weeks 1, 2, and 3. By week 4 patient 1 has a DLT and we initiate the TITE-CRM with patients 4, 5, 6, and 7 being assigned dose level 1. With no DLTs, at week 7 the dose is escalated and patients 8, 9, 10 and 11 are assigned to dose level 2. With no DLTs, by week 12 the dose is escalated again and patient 12 is assigned to dose level 3. Patient 12 has a DLT and the dose is de-escalated with patient 13 to 18 being assigned to dose level 2, with two DLTs being observed among them. The estimated MTD is dose level 2 with an estimated probability of DLT of 0.27 and 90% probability interval of (0.12, 0.44). Two of the 10 patients assigned to dose level 2 have DLTs. With an accrual rate of 4 patients per month, this study takes a total of less than 6 months to complete.

4.1.1.1 Dose Limiting Toxicities for Phase 1

All patients who receive at least one dose of cobimetinib and hydroxychloroquine, with or without atezolizumab, will be evaluable for toxicity.

In order for a patient to be evaluable for DLT assessments, the patient must either incur a DLT during the DLT evaluation period, or have received at least 80% of the planned doses of hydroxychloroquine, cobimetinib, and if applicable, atezolizumab. Patients who do not fulfill one of these criteria should be considered non-evaluable for DLT assessment purposes, and be replaced.

A DLT is defined as an AE that is possibly, probably, or definitely related to study drug administration, and that is:

- Not due to the underlying malignancy;
- Has no clear evidence of an alternative etiology; and
- Meets one of the following CTCAE v.5.0 criteria during the first 28 days of hydroxychloroquine, cobimetinib, and if applicable, atezolizumab administration:
 - Any Grade ≥ 4 hematologic toxicity, except grade 4 lymphopenia, lasting ≥ 7 consecutive days
 - Grade 3 neutropenia with fever
 - Grade 3 thrombocytopenia with clinically significant bleeding
 - Any circumstance that results in dose reduction

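### The planned Phase 1 safety summary covers only treatment-related toxicity, so the analysis of the secondary safety objective omits every event judged unrelated

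*Combined protocol and SAP*

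**What the plan says.** The Phase 1 secondary objective in section 1 is "To evaluate the safety profile of the combination of cobimetinib, atezolizumab, and hydroxychloroquine" in KRAS-mutated advanced malignancies.

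The analysis plan addresses safety in two places:

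- **Section 4.1.1.3 (primary endpoint).** The TITE-CRM estimates the DLT probability at each dose, and "the observed rate of DLT will be reported by dose level". Under section 4.1.1.1, "A DLT is defined as an AE that is possibly, probably, or definitely related to study drug administration", and the event must fall in the first 28 days.
- **Section 4.1.1.4 (secondary endpoints).** "Treatment-related toxicity will be reported by type, frequency, and severity", using CTCAE version 5. Nothing further is said about adverse events: no all-cause table, no summary of serious events or deaths, and no breakdown by dose.

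The toxicity population is wide: "All patients who receive at least one dose of cobimetinib and hydroxychloroquine, with or without atezolizumab, will be evaluable for toxicity" (section 4.1.1.1). For response, section 4.1.1.4 is more specific: "The frequency of radiographic response will be documented with summary statistics at the estimated MTD and by dose level".

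**The concern.** The objective asks for a safety profile. The planned summary delivers the part of it that investigators attribute to the drugs. Since DLTs must also be related, every planned Phase 1 safety result depends on attribution.

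Attribution is hard to make and impossible to check here. There is no control group, patients have advanced, previously treated cancer, and they receive two or three drugs at once. A new toxicity of the combination that resembles disease or intercurrent illness could be classed as unrelated and never reach the table.

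At stake is how complete the safety result is. Phase 2 is to be "amended after preliminary safety and efficacy results from phase 1 and other ongoing clinical trials have been analyzed and a summary incorporated" in the protocol (section 4.1.2), so the Phase 1 safety results feed a real decision.

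**Working it through.** The plan states no figure on this point, so the check is mainly textual: does any other section supply an all-cause Phase 1 safety analysis?

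**1. Is the restriction explicit?** Yes. Section 4.1.1.4 names treatment-related toxicity. Sections 9.1.1, 9.2 and 9.4.1.7, by contrast, require adverse events and gradable laboratory abnormalities to be recorded whatever their attribution. Collection is all-cause; the analysis is not.

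**2. How is relatedness decided?** Section 9.3 uses an investigator's Yes or No. Grounds for No include pre-existing conditions, underlying disease, intercurrent illness and concomitant medication. Two loose ends add to the uncertainty:
- The DLT definition uses a graded scale (possibly, probably, definitely) while section 9.3 uses Yes/No. Section 4.1.1.4 does not say which one defines treatment-related.
- The line in section 9.3 on describing each event asks for its relationship to atezolizumab and/or cobimetinib and leaves out hydroxychloroquine, although the guidance beneath it includes that drug.

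An all-cause table does not depend on settling either.

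**3. Does the DLT analysis fill the gap?** No. It also requires relatedness, and its window is 28 days (the synopsis puts it at the end of Cycle 2; either way, later events fall outside). Section 4.1.1 notes that hydroxychloroquine eye toxicity appears at high cumulative doses.

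**4. Does any other output fill it?**

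| Section | What it provides | All-cause analysis? |
|---|---|---|
| 9.4.1.2 | Reporting of deaths regardless of attribution | No; case reporting |
| 9.4.5.3 | Expected adverse events in IND annual reports | No; regulatory reporting |
| 9.4.5.4 | Serious events to the DSMC within 24 hours | No; case reporting |
| 13.3 | DSMC report to sites on cumulative toxicities | Not specified |
| 13.5 | Toxicities and serious events summarized for the DSMC | Not specified |
| 1 and 4.1.2 | Phase 1 safety summary before the Phase 2 amendment | Content not specified |

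None plans an all-cause analysis for the secondary objective.

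**5. How many events are omitted?** This cannot be determined. Section 3.1.4.2 gives serious events in 40% and serious treatment-related events in 26% of patients on atezolizumab plus cobimetinib in an earlier phase 3 trial. That shows all-cause and related figures can differ. It is a different regimen and the denominator of the second figure is unclear, so it is not carried over to this trial.

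**6. What precision would a dose-level split have?** Table 2 gives the "average expected number of patients assigned to each dose based on the two stage TITE-CRM" for N=18. With no events in n patients, the exact two-sided 95% upper limit is 1 − 0.025^(1/n).

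| Scenario | Average n at levels 1/2/3 | Upper limit for 0 events |
|---|---|---|
| 1 | 11/4/3 | 28.5% / 60.2% / 70.8% |
| 2 | 6/6/6 | 45.9% at each level |
| 3 | 2/5/11 | 84.2% / 52.2% / 28.5% |

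Figures by level can only be descriptive.

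**The case against.** **The excluded class may be narrow.** Under section 9.3, No calls for evidence of another cause and/or no plausible timing. This stands as a limit on size: the number omitted could be small. It does not make the exclusion checkable.

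**Decisions do not hang on this sentence.** The MTD comes from the TITE-CRM. The Phase 2 amendment needs a safety summary that is not confined to related events, plus scientific review and IRB approval. Serious events and deaths reach the DSMC and other parties anyway. All of this stands, and it is why the point is a cheap improvement rather than a threat to the trial's validity. But those routes are case reporting and oversight; they do not specify the analysis of the secondary objective.

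**An all-cause table brings noise.** Section 9.1.1 generally keeps disease progression out of adverse events but counts new signs or symptoms of pancreatic adenocarcinoma, and at least 12 of the 18 evaluable patients are to have pancreatic or colorectal cancer. This stands as a cost. Showing the related subset alongside contains it.

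**A stronger reading: the plan pools dose levels and so hides triplet toxicity.** A reader might infer this because dose level 1 has no atezolizumab, the toxicity population spans both regimens, and no split is stated. Level 1 would hold on average 11, 6 or 2 of 18 patients (61%, 33%, 11%). If a 30% toxicity (an assumed rate) occurred only with atezolizumab, a pooled table would show 0.30 × 7/18 = 12%, 0.30 × 12/18 = 20% or 0.30 × 16/18 = 27%. The documents do not support the inference. They are silent on pooling, and the sentence on who is evaluable for toxicity does not define a table. With DLTs and response already reported by dose level, an analyst would probably do the same for toxicity. The largest dilution also arises in scenario 1, where level 1 is the true MTD and is selected 74% of the time, so the triplet would usually not go forward.

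**Conclusion.** The concern holds for the restriction to related events. Section 4.1.1.4 states it as a rule, and no other section plans an all-cause Phase 1 analysis. Followed as written, the result for the secondary safety objective omits every event judged unrelated.

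Its size in events or patients cannot be determined from the documents. The conclusion rests on reading the sentence literally and on treating case reporting and DSMC summaries as something other than the endpoint analysis.

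It does not follow that the MTD is biased or that data are lost: dose selection uses DLTs, and all adverse events are recorded. Nor does it follow that doublet and triplet patients will be combined. The missing dose-level split is a lapse in consistency with section 4.1.1.3 and with the response analysis, worth repairing in the same edit.

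**What to change.** Replace the toxicity sentence in section 4.1.1.4 with:

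> All adverse events with onset from first dose to 30 days after last study treatment, regardless of attribution, will be reported by type and maximum CTCAE v5 grade, by assigned dose level and at the estimated MTD, with the treatment-related subset shown alongside; later SAEs and AESIs (to 90 days after last atezolizumab) will be listed separately.

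Two details matter:

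- **One common window.** Section 9.4.5.1 cannot be borrowed whole. It extends follow-up for serious events and events of special interest to 90 days after the last atezolizumab dose, which level 1 never receives, and it admits procedure-related serious events before the first dose. Used for a table by dose, it could follow triplet patients for longer than doublet patients.
- **Assigned dose level.** Sections 8.1 and 8.2.2 allow cobimetinib to be reduced after the DLT period and later raised again, so dose received would be ambiguous.

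The cost is one sentence of wording. Events, grade, attribution and dose level are already collected. The drawbacks are longer tables, a higher headline adverse event rate that includes disease symptoms, and small numbers per level that support description only.
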